9.2. Endpoints

Additional details and definitions are provided in Section 11, Statistical Methods.

9.2.1. Primary Efficacy Endpoint

The primary efficacy endpoint of this study is the rate of RBC TI lasting at least 8 weeks. The 8-week RBC TI rate is defined as the proportion of subjects without any RBC transfusion during any consecutive 8 weeks (56 days) starting from Study Day 1. Study Day 1 is defined as the day of the first dose for subjects enrolled in Part 1 and the day of randomization for subjects enrolled in Part 2.

9.2.2. Secondary Endpoints

- Safety of imetelstat in subjects with MDS (eg, incidence, intensity, and type of adverse events, vital signs measurements, clinical laboratory values, ECGs changes, and deaths);
- 24-week RBC TI rate, defined as the proportion of subjects without any RBC transfusion during any consecutive 24 weeks (168 days) starting from Study Day 1;
- Time to the 8-week (24-week) RBC TI, defined as the interval from Study Day 1 to the first day of the first 8-week (24-week) RBC TI period;
- Duration of RBC TI, defined as the first day of the longest RBC TI period to the date of the first RBC transfusion after the TI period starts;
- Rate of hematologic improvement, including HI-E, per modified IWG 2006;
- Rates of CR, PR, or mCR per modified IWG 2006;
- OS, defined as the interval from Study Day 1 to death from any cause. Survival time of living subjects will be censored on the last date a subject is known to be alive or lost to follow-up;
- Progression free survival, defined as the time interval from Study Day 1 to the first date of disease progression or death from any cause, whichever occurs first. For subjects who do not have documented disease progression and who are still alive at the end of the study or clinical cutoff will be censored at the last disease evaluation date.
- Time to progression to AML, defined as the interval from Study Day 1 to the date of AML diagnosis. For subjects who have not progressed to AML and are still alive at the cutoff date for the analysis or who withdraw from the study (withdrawal of consent or lost to follow-up), data will be censored at the date of the last disease evaluation;
- Amount and relative change in RBC transfusions;
- Rate of myeloid growth factors usage, defined as the proportion of subjects receive any myeloid growth factors starting from Study Day 1; duration of myeloid growth factor administered starting from Study Day 1;
- Assessment of QUALMS, FACT-An, and EQ-5D-5L;

- Pharmacokinetic parameters (eg, C_{max} , AUC_{0-t}), and immunogenicity of imetelstat (eg, antibodies to imetelstat);
- Medical resource utilization data including hospitalization, emergency room visits, and hematology specialist visits ;
- ECG parameters including change in QT interval by Fridericia's correction method ($\Delta QTcF$) in the Ventricular Repolarization substudy (Part 2 only).

9.2.3. Exploratory

Exploratory endpoints are not applicable for subjects participating in the Ventricular Repolarization substudy (after Protocol Amendment 7);

- TA and hTERT at baseline and the change from baseline, TL at baseline only;
- Cytogenetic status at baseline and change over time for cytogenetic response;
- Mutation status at baseline and change over time including at the time of suspected response (CR, PR, mCR, HI-E [Hb]) or PD;
- Immune profiles at baseline and change from baseline (Part 1 only).

9.3. Efficacy

Evaluations of efficacy are based on the modified IWG Response Criteria for MDS, as revised in 2006 (see Attachment 5).⁷

9.3.1. Evaluations

Refer to Table 1 for Part 1 and Table 3 for the main study of Part 2 for a schedule of assessments. Subjects participating in the Ventricular Repolarization substudy after Amendment 7 will have study evaluations performed as per the Time and Events Schedule in Table 14 of Attachment 11. Study evaluations performed in the Extension Phase can be found in Table 5.

9.3.1.1. Transfusions

Transfusion data will be collected during the treatment and posttreatment periods throughout the study as specified in the Time and Event Schedules. Transfusion is monitored at each visit for imetelstat infusion (every 4-week cycle), at each disease evaluation visit, and at all unscheduled visits during treatment. During the posttreatment phase, transfusion data will be collected every 4 to 6 weeks until the first transfusion in follow-up. Enhanced operational monitoring will be implemented to seek transfusion information from other documented sources. Enhanced and continuous medical review will be implemented to identify any sudden but unsustained increase of Hb values and to query whether transfusion has occurred.

Data to be collected include the date of transfusion, number of units and type of blood products transfused and the pre-transfusion Hb and platelet count. Red blood cell transfusions may be administered based on Hb level, investigator's assessment of the subject's clinical signs and symptoms, and local clinical practice. As the volume of 1 unit of RBC transfusion may vary regionally, one unit is defined as the amount that is intended to raise Hb by approximately 1 g/dL

in an adult patient (ie, one standard pRBC unit or equivalent). The total number of RBC units required over rolling 8-week time periods will be calculated to identify subjects who achieve RBC TI or transfusion reduction.

9.3.1.2. Hemoglobin Assessment

Hemoglobin levels will be measured as detailed in the Time and Event Schedules for Part 1 and Part 2 as per Table 1 and Table 3, respectively. For a given subject, the same local laboratory should be used for each hematology assessment throughout the study, to the extent possible. In Part 2, in addition to the local laboratory, a central laboratory will be used for all planned Hb assessments. Subjects enrolled in the Ventricular Repolarization substudy (after Protocol Amendment 7) are not required to send samples for central Hb laboratory assessments. Treatment decision and investigator-assessed disease response evaluations will be based on the local laboratory results (see Section 11.13 for adjudication of assessments by independent review). Sponsor assessed HI-E will primarily be based on the central laboratory results. Investigator- and sponsor assessments based on local laboratory data will also be presented.

Hematologic improvement-erythroid (HI-E) response is defined as i) a Hb rise of at least 1.5 g/dL above the pretreatment level and lasts at least 8 weeks or ii), reduction of at least 4 units of RBC transfusion units/8 weeks compared with the prior RBC transfusion burden (criterion adapted from the modified IWG 2006 [Attachment 5]). Pretreatment Hb level is defined as the average of all the Hb values in the 8 weeks prior to C1D1, including the value on C1D1 (Part 1 or Part 2) and excluding values that were within 14 days after transfusion (thus considered to be influenced by transfusion). If there were no Hb values that met this definition of not being influenced by transfusions, then the baseline value is used.

9.3.1.3. Bone Marrow Assessment

Bone marrow aspirate and biopsy must be performed as detailed in the Time and Event Schedules for Part 1 and the main study of Part 2 as per Table 1 and Table 3, respectively. Bone marrow aspirate and biopsy must be available for submission for central pathology review prior to the Randomization in the main study of Part 2 to confirm diagnosis and eligibility for study. Central pathology review is not required for subjects participating in the Ventricular Repolarization substudy (after Protocol Amendment 7).

Central Pathology Review (Main Study of Part 2)

A sample of the baseline bone marrow aspirate and biopsy must be submitted to the Independent Central Pathology Reviewer for diagnostic confirmation. These samples will consist of bone marrow aspirate smears, peripheral blood smears, and bone marrow biopsy (either in formalin or unstained recut sections). (Refer to the manual for further instructions on sample preparation, handling and shipping.)

All subsequent bone marrow samples performed for Disease Evaluations, including those at the time of suspected response (CR, PR, or mCR in subjects with >5% baseline bone marrow aspirate blasts) and PD must be submitted for central review. These samples will consist of bone marrow aspirate smears, peripheral blood smears, and in the case of PD, bone marrow biopsy (either in

formalin or unstained recut sections). (Refer to the manual for further instructions on sample preparation, handling and shipping.)

Samples of bone marrow aspirate will be used for central cytogenetic assessment (refer to Section 9.5).

9.4. Pharmacokinetics and Immunogenicity

9.4.1. Sample Collection and Handling

Plasma samples (sparse sampling) will be collected from all subjects as described in the Time and Events Schedule for Pharmacokinetic Sampling for Part 1 (Table 2) and for the main study of Part 2 (Table 4). A serial sampling schedule was carried out in up to approximately 15 subjects before implementation of Amendment 2. In the Ventricular Repolarization substudy after Protocol Amendment 7, blood for PK samples will be collected on C1D1 prior to study drug administration through 8 hours after start of infusion (see schedule of events in Attachment 11).

Samples will be used to evaluate the pharmacokinetics as well as the immunogenicity of imeteostat (antibodies to imeteostat). Venous blood samples will be collected, and the plasma will be divided into 2 to 3 aliquots (1 aliquot for pharmacokinetic analysis, 1 aliquot for immunogenicity assessment [when appropriate], and 1 aliquot as a back-up). Samples collected for analyses of imeteostat plasma concentration and antibodies to imeteostat may additionally be used to evaluate safety or efficacy aspects that address concerns arising during or after the study period, for further characterization of immunogenicity or for the evaluation of relevant biomarkers or metabolites of imeteostat. Genetic analyses will not be performed on these samples. Subject confidentiality will be maintained.

The exact dates and times of blood sampling must be recorded. Refer to the Laboratory Manual or equivalent document for sample collection requirements. Collected samples must be stored under the specified and controlled conditions for the temperatures indicated in the Laboratory Manual.

9.4.2. Analytical Procedures

Pharmacokinetics

Plasma samples will be analyzed to determine concentrations of imeteostat using a validated, specific, and sensitive hybridization enzyme-linked immunosorbent assay method by or under the supervision of the sponsor. Only samples from imeteostat treated subjects will be analyzed for imeteostat concentration.

Immunogenicity

The detection and characterization of antibodies to imeteostat will be performed using a validated assay method by or under the supervision of the sponsor. All plasma samples collected for detection of antibodies to imeteostat will also be evaluated for imeteostat plasma concentration to enable interpretation of the antibody data. Only samples from imeteostat treated subjects will be analyzed for immunogenicity and corresponding imeteostat concentration.

9.4.3. Pharmacokinetic Parameters

Intensive Pharmacokinetic Sample Analysis

Pharmacokinetic parameters (C_{\max} , AUC_{0-t}) will be derived, for subjects in Part 1 (up to approximately 15 subjects), from plasma concentration versus time data for imetelstat, but more parameters may be estimated if needed. The pharmacokinetic parameters for imetelstat are defined as follows:

C_{\max} Maximum observed plasma concentration

AUC_{0-t} Area under the plasma concentration-time curve from time 0 to t

More parameters may be estimated if warranted by the data.

Sparse Pharmacokinetic Sample Analysis

Descriptive statistics (geometric and arithmetic means, standard deviation, coefficient of variation [%]) will be provided to summarize imetelstat plasma concentrations at each sampling time point for both Part 1 and the main study of Part 2. Population pharmacokinetic analysis will be performed to estimate pharmacokinetic parameters such as clearance and volume of distribution. In addition, exposure parameters (eg, C_{\max} or AUC) may be selected to further explore pharmacokinetic-pharmacodynamic relationships between exposure and relevant pharmacodynamic, or biomarker information.

9.4.4. Immunogenicity Assessments

Antibodies to imetelstat (anti-drug antibodies) will be evaluated in all subjects in Part 1 and the main study of Part 2 according to the Time and Events Schedules (Table 1 and Table 3).

Samples will be used to evaluate the pharmacokinetics as well as the immunogenicity of imetelstat (antibodies to imetelstat) (see Section 9.4.1). If possible, any time an infusion-related reaction is observed during the study, an unscheduled blood sample should be drawn as soon as possible after the reaction for potential immune response analysis. These samples will be tested by the sponsor or sponsor's designee. Plasma samples will be screened for antibodies binding to imetelstat and the titer of confirmed positive samples will be reported. Other analyses may be performed to verify the stability of antibodies to imetelstat and/or further characterize the immunogenicity of imetelstat.

9.5. Biomarkers

Subjects enrolled in the Ventricular Repolarization substudy (after Amendment 7) are not required to have biomarker assessments performed.

Telomerase Activity and Telomere Length Analyses:

Baseline (predose on Day 1 of Cycle 1) peripheral blood samples will be collected from all subjects in both Part 1 and Part 2, and on-treatment peripheral blood samples will be collected from all subjects, as outlined in the Time and Events Schedules (Table 1 and Table 3), to isolate leukocytes

and analyze TA. Baseline (C1D1 predose) samples will be collected to analyze TL in Part 1 and Part 2 as outlined in Table 1 and Table 3.

hTERT RNA Expression Analysis:

Baseline (C1D1 predose) peripheral blood samples will be collected from all subjects in both Part 1 and Part 2. Additional on-treatment peripheral blood samples will be collected from all subjects as outlined in the Time and Events Schedules (Table 1 and Table 3) to assess hTERT level.

Mutation Analysis:

Peripheral blood samples will be collected from all subjects as outlined in the Time and Events Schedules (Table 1 and Table 3) for mutation analysis. For Part 1, blood samples at baseline and at the time of suspected response (CR, PR, mCR, HI-E [Hb]) or PD will be collected to evaluate the change of mutation. For Part 2, blood samples will be collected at baseline, every 12 weeks after C1D1, at time of suspected response (CR, PR, mCR, HI-E [Hb]) or PD. Genomic DNA will be prepared from blood to characterize mutation status on a panel of MDS related genes by next-generation sequencing or other methodology to evaluate the association of baseline mutation status and the change of mutation with clinical response.

Immunophenotype Analysis (Part 1 only):

Blood samples will be collected from all subjects as outlined in the Time and Events Schedules (Table 1 and Table 3) and may be used to explore imetelstat effects on myeloid progenitor cells differentiated into terminal functional myeloid cells by immunophenotyping and functional profiling using flow cytometer or cytometry by time of flight (CyTOF) or similar assays. A portion of the previously collected blood samples may be used to evaluate imetelstat effects on key cytokine and chemokines that are involved in inflammation, immune response, and repair by immuno-multiplexing analysis or other methodology where necessary.

Cytogenetic Analysis:

Bone marrow aspirate samples will be collected from all subjects as outlined in the Time and Events Schedules (Table 1 and Table 3) for karyotype analysis to characterize cytogenetics at screening to correlate with clinical response.

For subjects with a cytogenetic abnormality at baseline, follow up samples should be collected every 24 weeks after C1D1, at the time of suspected CR or PR and every 24 weeks thereafter up to and including PD to evaluate eradication or reduction of a pre-existing abnormality for assessing cytogenetic response. For subjects with a normal baseline cytogenetic result, a sample should be collected at disease progression to evaluate appearance of a new abnormality for assessing possible mechanisms of progression. Peripheral blood may be submitted in place of an aspirate only if a bone marrow aspirate cannot be obtained (eg, dry tap). The same sample type collected at screening must be collected throughout the subject's participation in the study when possible. Sites will be provided with the baseline result report to determine what follow up samples should be collected.

Bone marrow sampling for cytogenetics on treatment is not required for subjects participating in the Ventricular Repolarization substudy (after Protocol Amendment 7).

Bone marrow aspirate for RNA Seq or CyTOF:

If sufficient sample is obtained, bone marrow aspirates may be characterized by technologies such as quantitative real-time polymerase chain reaction (qRT-PCR), gene expression profiling, microRNA, methylation, mutation, RNA sequencing and CyTOF analyses or other similar technologies utilized for analysis of RNA expression or proteins. Bone marrow sampling for RNA Seq or CyTOF is not required for subjects participating in the Ventricular Repolarization substudy (after Protocol Amendment 7).

Stopping Analysis

Biomarker analyses are dependent upon the availability of appropriate biomarker assays and clinical response rates. Samples will be collected only at sites where local regulations and shipping logistics permit. Biomarker analysis may be deferred or not performed, if during or at the End of the Study, it becomes clear that the analysis will not have sufficient scientific value for biomarker evaluation, or if there are not enough samples or responders to allow for adequate biomarker evaluation. In the event the study is terminated early or shows poor clinical efficacy, completion of biomarker assessments is based on justification and intended utility of the data. Additionally, if sufficient pharmacodynamic information is obtained from TA, TL and hTERT testing of at least 30 subjects, further on-treatment sample collections may cease, without requiring a protocol deviation or waiver.

9.6. Patient Reported Outcomes (Part 2 Only)

Patient-reported outcomes will be assessed in subjects with MDS at the visits indicated in the Time and Events Schedule (Table 3) using the PRO measures described below. The questionnaires and instructions will be provided as separate paper documents, and subject responses will be transcribed to the eCRF by site staff. The protocol assessment questionnaires need to be done in the same order at each visit and for each subject to ensure that the subject is answering these as consistently as possible. At all visits, the questionnaires should be completed before any tests, procedures, dosing, or other consultations are performed and before the subject is informed of any assessment results (eg, Hb values), when possible. Subjects should be provided a private, quiet area to complete the questionnaires. During the posttreatment period, if the questionnaires are conducted over a telephone call with the subject, then the subject's questionnaire responses will be read over the telephone to the site staff who will record the data in the questionnaires. If the subject is unable to complete the assessment during the EOT visit, then the reason for not completing the questionnaire will be documented (eg, too ill, subject refused). The study site staff should instruct the subject to carefully read the instructions and questions of the PRO instrument(s) prior to marking responses, that there are no right or wrong answers, and that their responses to the questionnaire will not be used to determine their study eligibility.

PRO evaluation is not required for subjects participating in the Ventricular Repolarization substudy (after Protocol Amendment 7).

The **EQ-5D-5L** is a generic measure of health status (Attachment 7). For purposes of this study, the EQ-5D-5L will be used to generate utility scores for use in cost-effectiveness analyses. The EQ-5D-5L is a 5-item questionnaire that assesses 5 domains including mobility, self-care, usual activities, pain/discomfort and anxiety/depression plus a visual analog scale rating “health today” with anchors ranging from 0 (worst imaginable health state) to 100 (best imaginable health state).^{8,29} The scores for the 5 separate questions are categorical and cannot be analyzed as cardinal numbers. However, the scores for the 5 dimensions are used to compute a single utility score ranging from zero (0.0) to 1 (1.0) representing the general health status of the individual.

The **FACT-An** (version 4) is one of the scales from the Functional Assessment of Chronic Illness Therapy Measurement System (Attachment 6). It consists of the FACT-G (General version) and 20 questions labeled “Additional concerns” which measure anemia/fatigue.

The FACT-G (version 4) is a 27-item compilation of general questions divided into 4 primary quality-of-life domains:

- Physical well-being
- Social/family well-being
- Emotional well-being
- Functional well-being

The FACT-G (version 4) is considered appropriate for use with subjects with any form of cancer and has also been used and validated in other chronic illness conditions. The additional items of the FACT-An allow for constructing a Fatigue subscale. The subject is asked to rate the scale items as it applies to the past 7 days, on a 5-point scale (0=Not at all, 1=A little bit, 2=Somewhat, 3=Quite a bit, 4=Very much). Negatively stated items will be reversed by subtracting the response from 4. After reversing the proper items, items are summed to a total to generate a score on a (sub)scale.^{6,53}

The **QUALMS**¹ is a 38-item measure that assesses health-related quality of life for subjects with MDS (Attachment 8). Thirty-three items are used to calculate the total score, as well as the 14-item physical burden (QUALMS-P), 3-item benefit-finding (QUALMS-BF), and 11-item emotional burden (QUALMS-E) subscales. There are also 5 single-item questions presented at the end of the measure that do not form part of the overall scale, as they are not applicable to all subjects with MDS.

The **PGIC** is used to capture the patient’s perspective of improvement or decline in MDS over time (Attachment 9). The PGIC has a 7–point response scale ranging from 1 (very much improved) to 7 (very much worse), with 4 representing no change. It will be used as one of the anchors for certain psychometric performance tests and estimating meaningful important difference.

9.7. Medical Resource Utilization (Part 2 Only)

Medical resource utilization data, associated with medical encounters, will be collected in the eCRF in Part 2 by the investigator and study-site personnel for all subjects throughout the study from the time of first dose until EOT visit or 30 days after the last dose of study drug, whichever occurs later. Medical resource utilization data collection is not required for subjects participating in the Ventricular Repolarization substudy (after Protocol Amendment 7).

Protocol-mandated procedures, tests, and encounters are excluded. The data collected may be used to conduct exploratory economic analyses and will include:

- Frequency and duration of hospitalization (total days length of stay, including duration by wards; eg, intensive care unit)
- Outpatient medical encounters and treatments (including physician or emergency room visits, selected tests and procedures, and medications)

9.8. Safety Evaluations

All subjects who receive at least 1 dose of study drug will be considered evaluable for toxicity. Any clinically relevant changes occurring during the study must be recorded in the eCRF. Any clinically significant abnormalities persisting at the end of the study/early withdrawal will be followed by the investigator until resolution or until a clinically stable endpoint is reached. The study will include the following evaluations of safety and tolerability according to the time points provided in the Time and Events Schedule for Part 1 and Part 2 (Table 1 and Table 3, respectively).

Adverse Events

Adverse events will be reported by the subject (or, when appropriate, by a caregiver, surrogate, or the subject's legally acceptable representative) for the duration of the study. Adverse events will be followed by the investigator as specified in Section 12 Adverse Event Reporting. Adverse events will be reported and graded according to the National Cancer Institute Common Terminology Criteria for Adverse Events (NCI-CTCAE), Version 4.03.

Adverse Events of Interest (AEI)

Specific adverse events or groups of adverse events will be followed as part of standard safety monitoring activities by the sponsor. These events will be reported to the sponsor within 24 hours of awareness irrespective of seriousness (ie, serious and non-serious adverse events) following the procedure described in the protocol for serious adverse events and will require enhanced data collection. The Imetelstat Questionnaire for Adverse Events Of Interest eCRFs must be completed for each AEI. For this study the adverse events of special interest are:

- ALT Grade ≥ 3 (>5.0 x ULN)
- AST Grade ≥ 3 (>5.0 x ULN)

- Bilirubin Grade ≥ 3 (>3.0 x ULN)
- ALP Grade ≥ 3 (>5.0 x ULN)
- All hepatic adverse events
- ALT or AST Grade ≥ 2 (>3.0 x ULN) **WITH** Bilirubin Grade ≥ 2 (>2.0 x ULN)

For these events, laboratory assessments should be repeated once or twice weekly until bilirubin with fractionation return to baseline levels. Additionally, subjects with Grade 1 and Grade 2 treatment-emergent elevations in AST, ALT, ALP and bilirubin at the time of treatment discontinuation should continue to have laboratory assessments monthly until resolution to at least baseline or until the start of subsequent therapy, whichever comes first. All hepatic adverse events and LFT abnormalities will be reviewed by an Independent Hepatic Expert Committee, at least quarterly, and as needed.

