Chemistry panel for LFT investigations (local laboratory)	Includes GGT, chloride, bicarbonate, magnesium, and fractionated bilirubin. For subjects with AST, ALT, ALP or bilirubin Grade \geq 3, repeat chemistry panel and LFT investigations panel weekly until bilirubin with fractionation is $<$ 3x ULN, and AST, ALT and ALP is $<$ 5x ULN. Subjects with Grade 1 or Grade 2 elevations in AST, ALT, ALP or bilirubin at time of treatment discontinuation should continue to have tests monthly until resolution to at least baseline grade or until the start of subsequent therapy, whichever comes first.							If an adverse event of interest occurs
INR (or PT) and aPTT (local laboratory)	With additional assessments performed during treatment phase if subject has a hemorrhagic event.	X						Repeat during study if subject has a Grade \geq 3 bleeding event
Serum EPO level (local laboratory)	Only required during treatment at first suspected response. Repeat assessment is not required if response further improves.	X						At time of suspected HI-E (Hb), PR, CR

Table 3 Continued: Time and Events Schedule for Part 2, Main Study (Double-blind, Randomized 2:1, Imetelstat or Placebo Treatment)

Study Procedures	Comments	Screening Phase	Treatment Phase (4-week cycles \pm 3 days)					Posttreatment Follow-up Phase
		Up to 28 days before Randomization	Cycle 1 Day 1 (predose)	Cycle 1 Day 8, 15, 22	Cycle 2 Day 1, 8, 15, 22	Cycle 3 until EOT Day 1	EOT Visit 30 \pm 3 days after last dose	Survival Follow-up Every 12-16 weeks
Serum ferritin, transferrin saturation (local laboratory)	Total iron binding capacity and serum iron (Fe) may be performed to calculate transferrin saturation if transferrin saturation is not available at the site.	X	X		X (D1 only)	X	X	
B12 / folic acid / reticulocytes (local laboratory)		X						
Hepatitis serologies	Comprehensive hepatitis serology panel A through E. Hepatitis D serology is only required if the subject tests positive for the hepatitis B surface antigen (HBsAg). If the subject screening window is >28 days (Section 9.1.3), hepatitis screening results may still be used to determine eligibility outside of the initial 28-day screening period provided the subject is asymptomatic and does not meet Exclusion Criteria no. 12 (Section 4.2).	X						
Serum or urine pregnancy test		X			X (D1 only)	X	X	
Pharmacokinetics, Pharmacodynamics and Immunogenicity								

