^a Extensive investigation includes repeating liver enzyme and serum bilirubin tests with fractionation once or twice weekly until levels return to baseline. Obtain additional tests to evaluate liver function, as appropriate (i.e., INR, albumin). In addition, obtain a detailed history of symptoms, prior or concomitant disease, concomitant medications (including nonprescription herbal and dietary supplements), alcohol use, recreational drug use, special diets and environmental chemical agents. The following should be ruled out: acute viral hepatitis types A, B, C, D and E; autoimmune or alcoholic hepatitis; nonalcoholic steatohepatitis (NASH); hypoxic/ischemic hepatopathy; and biliary tract disease and may require gastroenterology and hepatology consultations. Consider hepatology (or gastroenterology) consultation. Document findings in the Imetelstat Questionnaire for Adverse Event of Interest eCRF.

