12.3.3.1. Elevated Liver Function Tests (LFTs)

Elevations in the following LFTs will be captured as adverse events of interest:

- ALT Grade ≥ 3 (>5.0 x ULN)
- AST Grade ≥ 3 (>5.0 x ULN)
- Bilirubin Grade ≥ 3 (>3.0 x ULN)
- ALP Grade ≥ 3 (>5.0 x ULN)
- ALT or AST Grade ≥ 2 (>3.0 x ULN) **WITH** Bilirubin Grade ≥ 2 (>2.0 x ULN)

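### The LFT-panel rows of Tables 3, 5 and 14, Section 9.8 and Table 10 footnote a give different triggers and stop rules for repeat liver tests

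*Protocol*

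**What the plan says.** Section 9.8 lists the adverse events of interest: ALT, AST or ALP above 5x ULN, bilirubin above 3x ULN, all hepatic adverse events, and the combined event of ALT or AST above 3x ULN with bilirubin above 2x ULN (both Grade 2 or higher). For all of these it continues: "laboratory assessments should be repeated once or twice weekly until bilirubin with fractionation return to baseline levels". The only stop it gives is therefore the return of fractionated bilirubin to baseline. Section 12.3.3.1 repeats the laboratory part of the list under the words "Elevations in the following LFTs will be captured as adverse events of interest".

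The row for the LFT investigations panel in Table 3 (main study) is scheduled "If an adverse event of interest occurs". Its rule for repeats opens "For subjects with AST, ALT, ALP or bilirubin Grade" 3 or higher, and tells the site to "repeat chemistry panel and LFT investigations panel weekly until bilirubin with fractionation is" below 3x ULN and AST, ALT and ALP are below 5x ULN. Table 5 (Extension Phase) and Table 14 (QTc substudy) carry the same rule.

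Section 6.1.3 sets dose-modification actions for Grade 3 or 4 AST, ALT or bilirubin, Grade 3 or 4 hepatic adverse events, and the combined event, when present at the planned start of a cycle. Footnote a of its Table 10 says: "Extensive investigation includes repeating liver enzyme and serum bilirubin tests with fractionation once or twice weekly until levels return to baseline".

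**The concern.** One liver event can fall under three instructions that do not agree on when repeat testing starts or ends. What a site does then depends on which page it follows. The combined event is the sharpest case: it is defined at Grade 2 or higher, while the schedule rows act only from Grade 3.

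This matters because Section 1.1.5.2.3 names LFT abnormalities and clinical hepatic events as the adverse events of concern. It adds that severe hepatobiliary events have been seen for which a relationship to imetelstat cannot be excluded. A site that followed the LFT-panel row as printed would test less often than Section 9.8 asks.

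**Working it through.** There is no sample size or power figure to reproduce. The check sets the rules side by side and then puts values through them.

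| Source | Trigger | Frequency | Stop |
|---|---|---|---|
| LFT-panel row, Tables 3, 5, 14 | AST, ALT, ALP or bilirubin at Grade 3 or higher | Weekly | Bilirubin <3x ULN and AST, ALT, ALP <5x ULN |
| Section 9.8 | Every listed event of interest | Once or twice weekly | Bilirubin at baseline; no enzyme named |
| Table 10 footnote a | Table 10 events present at the planned start of a cycle | Once or twice weekly | Liver enzymes and bilirubin at baseline |

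Table 1 has the same row as Table 3, but all Part 1 subjects have stopped treatment, so the live conflict is in Tables 3, 5 and 14.

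**Case 1: combined event at its Grade 2 level.** Take ALT 4x and bilirubin 2.5x ULN, with ALP below 5x ULN and bilirubin above that subject's baseline.
- Section 9.8: 4 > 3 and 2.5 > 2, so it is an event of interest. Repeats are due, and bilirubin has not met the stop.
- LFT-panel row: 4 is not above 5 and 2.5 is not above 3, so nothing is at Grade 3 and weekly repeats are not triggered. Also 4 < 5 and 2.5 < 3, so the stop is already met at onset.
- Footnote a: repeats are due if the event is present at the planned start of a cycle; otherwise the footnote does not apply.

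The same holds across the Grade 2 band (ALT or AST above 3x to 5x, bilirubin above 2x to 3x), except that values exactly at 5x or 3x do not meet the row's stop. If either component reaches Grade 3, the row does trigger weekly repeats.

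**Case 2: isolated ALT or AST above 5x ULN, bilirubin at baseline.**
- Section 9.8: an event of interest, but its only stop condition is met at onset.
- LFT-panel row: weekly until below 5x ULN.
- Footnote a, at a planned cycle start: until enzymes reach baseline.

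**Case 3: a Grade 3 transaminase event that has fallen to 4x ULN, still above baseline, with bilirubin and ALP under the row's limits.**
- LFT-panel row: weekly testing ends.
- Footnote a: testing continues.
- Section 9.8: testing continues only while bilirubin is above baseline.

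**Frequency.** Weekly testing satisfies once or twice weekly, so the three rules can be met together on this point.

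**When Case 1 matters.** In Table 3, chemistry is scheduled on Days 1, 8, 15 and 22 of Cycle 1, so weekly tests occur then in any case. From Cycle 2 it is on Day 1 only. Suppose an unscheduled test on Day 8 of a later cycle shows the event. The LFT-panel row gives one panel for the event. The next scheduled chemistry is at Day 1 of the next cycle, Day 29 on the same count: 29 - 8 = 21 days later, against at most 7 days under Section 9.8.

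**The case against.** The strongest reply is that the protocol already orders the repeats. Section 9.8 lists the combined event and requires testing for it, and the routine chemistry rows of Tables 3, 5 and 14 send sites to 9.8. The LFT-panel row itself calls for a panel at any event of interest. An event found at a Day 1 visit and still present at dosing falls under Table 10: drug is held, footnote a requires repeats, and any restart needs recovery to baseline, which cannot be shown without tests. Grade 1 or 2 elevations at treatment discontinuation are tested monthly. Section 9.8.1 asks for the value supporting recovery when a laboratory abnormality is reported as an adverse event, and events of interest reach the sponsor within 24 hours.

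Most of this stands, and it rules out three stronger readings.
- A reader might infer that the combined event may get no repeat testing at all. It would not: what can be lost is the event-driven weekly repeat, at a site using only the LFT-panel row.
- A reader might infer a conflict in frequency. There is none.
- A reader might infer that duration data seen by the hepatic committee would be distorted. Section 11.12 names no duration measure, and SAP Section 4.10.3 summarises LFT duration for grade 3 or 4 only. The row's stop thresholds are the Grade 3 cut-offs, so its earlier stop does not cut that summary short.

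The safeguards do not remove the conflict. The LFT-panel rows carry no pointer to 9.8, and 9.8 refers sites back to the time points in the schedule. Table 10 does not reach a mid-cycle event, and the monthly tests apply only at discontinuation. None of them settles which stop rule governs Cases 2 and 3.

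**Conclusion.** The point holds as an internal contradiction in trigger and stop rule. The LFT-panel rows omit the Grade 2 combined event, which Section 9.8 includes. The stop rule of 9.8 ignores the enzymes, which the rows and footnote a both use. The rows also stop at fixed multiples of ULN, where the other two passages use baseline.

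The exposure is narrow: mainly Grade 2 combined events found mid-cycle from Cycle 2 onward, or at or after end of treatment, at a site that reads only the LFT-panel row. The documents give no rate for such events and do not show that sites follow the row alone, so no number of affected subjects can be stated. The nearest figure is for Grade 3 LFT elevations, seen in 3 of the 38 target-population subjects in Part 1 (8%). That bears on Cases 2 and 3, not on Case 1.

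Case 1 assumes that bilirubin has risen above that subject's baseline; the entry criteria allow total bilirubin up to 3x ULN, so this need not be so for everyone. Which rule is clinically right is not judged here. The correction is worth making because hepatic safety is a named concern and the change is small.

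**What to change.** Reconcile the LFT-panel rows of Tables 3, 5 and 14, Section 9.8 and Table 10 footnote a so that, for each listed liver event of interest, the trigger and the stop rule agree wherever they are stated. The sponsor decides which rule applies. Say explicitly what governs the combined event when it is found mid-cycle, and whether the stop refers to bilirubin, to enzymes or to both. Add a cross-reference to Section 9.8 in the LFT-panel rows.

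The cost is protocol wording and, depending on the rule chosen, possibly some extra local blood tests. No planned efficacy analysis changes.
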